9.1 General Principles

The objective of the data screening is to assess the quantity, quality, and statistical characteristics of the data relative to the requirements of the planned analyses.

9.2 Data Handling and Electronic Transfer of Data

The Amgen Global Study Operations-Data Management (GSO-DM) department will provide all data to be used in the planned analyses. This study will use the RAVE database.

All data collected in the eCRF will be extracted from RAVE. Protocol deviations will be transferred from eClinical. An Analysis Dataset for PK Concentrations (ADPC) will be provided to PKDM from Biostatistics. Unblinded subject and box ID randomization lists will be provided by Amgen's randomization group and the IVRS/IWRS when the study stops. Details on data transfer will be provided in the Data Transfer Plan.

9.3 Handling of Missing and Incomplete Data

9.3.1 Patterns of Missing Data

Subjects may be missing specific data points for various reasons. In general, data may be missing due to a subject's early withdrawal from study, a missed visit, or non-evaluability of a data point or an endpoint at a particular point in time. In the Data Quality Review (DQR) process, queries will be made to the sites to distinguish true

missing values from other unknown values (eg, due to measurement or sample processing error). All attempts will be made to capture missing or partial data for this trial prior to the database lock.

The frequency and pattern of missing data for efficacy endpoints will be assessed through descriptive summaries of the measurements over time.

9.3.2 Missing Lipid Measurements

For efficacy endpoints, where the primary analysis method is repeated measures linear effects model then missing lipid measurements will not be imputed.

The handling of missing LDL-C response (achievement of LDL-C < 70 mg/dL) is provided in [Section 6.3](#).

9.3.3 Handling of Incomplete Dates

Adverse event and concomitant medication with completely or partially missing start dates will be queried. After the issue is queried, the date is still incomplete with year only or year and month only, the start date will be imputed as described in [Table 1](#) below.

Table 1. Imputation Rules for Incomplete Dates

	Missing	Imputation	Exception
Start date (AE and concomitant medication)	Day	1	Default to Study Day 1 if an event starts the same year and month as Study Day 1
	Day / Month	1-Jan	Default to Study Day 1 if an event started the same year as Day 1

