6.1 Study Time Points

Enrollment Date

Enrollment date is the same as randomization date.

Randomization Date

The date a subject is randomized in the interactive voice/web response system (IVRS/IWRS) as recorded on the eCRF.

First Dose Date of SC Investigational Product of Blinded Period (First SCBIPD)

For each subject, the First Dose Date of SC Investigational Product is defined as the first administration date of the SC IP as recorded on the blinded period IP administration eCRF.

First Dose Date of Oral Investigational Product of Blinded Period (First POBIPD)

For each subject, the First Dose Date of Oral Investigational Product is defined as the first start date of the oral IP as recorded on the blinded period oral IP administration eCRF.

First Dose Date of SC Investigational Product of Open Label Extension OLE (First SCOLEIPD)

For each subject who participates in the open label extension (OLE) period of the study, the First Dose Date of SC Investigational Product of OLE is defined as the first administration date of the SC IP of OLE as recorded on the IP administration in OLE eCRF.

Blinded Period Day 1

For each randomized subject, Blinded Period Day 1 is defined as the first day that protocol-specified investigational product of blinded period is administered to the subject, which is the earlier of the first SCBIPD and the first POBIPD.

Open Label Extension OLE Day 1

For each subject who participates in OLE of the study, OLE Day 1 is defined as the first SCOLEIPD.

Study Day 1

Study day 1 is defined as Blinded period day 1.

Blinded Period Day

For each randomized subject, and for a given date of interest, blinded period day is defined as the number of days since Blinded Period Day 1:

Blinded period day = (date of interest (in Blinded Period) – Blinded Period Day 1 date) + 1.

If the date of interest is prior to the Blinded Period Day 1:

Blinded period day = (date of interest (in Blinded Period) – blinded period Day 1 date), so that the day prior to Blinded Period Day 1 is Blinded Period day -1.

OLE Day

For each subject who participates in OLE of the study, and for a given date of interest, OLE Day is defined as the number of days since OLE Day 1:

OLE Day = (date of interest – OLE Day 1 date) + 1.

If the date of interest is prior to the OLE Day 1:

OLE Day = (date of interest – OLE Day 1 date), so that the day prior to OLE Day 1 is OLE Day -1.

Study Day

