6.3 Other Study Related Definitions

Analytical Study Week Assignments

Analytical windows will be used to assign parameter measurements to study weeks.

The algorithm is provided in [Appendix B](#).

Actual Treatment Group

A subject's actual treatment group is the randomized treatment group, unless the subject receives treatment throughout the study that is different than the randomized treatment group assignment, in which case the actual treatment group is the treatment received.

Investigational Product (IP)

Blinded Period:

SC IP includes evolocumab SC 140 mg Q2W, evolocumab SC 420 mg QM and their corresponding SC placebo.

Oral IP includes ezetimibe PO 10 mg QD and placebo PO QD.

OLE: SC IP includes evolocumab SC 140 mg Q2W and evolocumab SC 420mg QM.

SC IP Exposure Period (Months) in Blinded Period

For each Q2W subject:

SC IP Exposure Period in Blinded Period = [min (EOS Date, the day before OLE day 1, Last SCBIPD + 14 days) - First SCBIPD + 1] / 365.25 * 12

For each QM subject:

SC IP Exposure Period in Blinded Period = [min (EOS Date, the day before OLE day 1, Last SCBIPD + 28 days) - First SCBIPD +1] / 365.25 * 12

Oral IP Exposure Period (Months) in Blinded Period

For each subject:

Oral IP Exposure Period = [min (EOS Date, the day before OLE day 1, Last POBIPD + 1 day) - First POBIPD + 1] / 365.25 * 12

SC IP Exposure Period (Months) in OLE

For each Q2W subject:

SC IP Exposure Period in OLE = [min (EOS date, last SCOLEIPD + 14 days) - First SCOLEIPD +1] / 365.25 * 12

For each QM subject:

SC IP Exposure Period in OLE = [min (EOS date, last SCOLEIPD + 28 days) - First SCOLEIPD +1] / 365.25 * 12

Study Exposure Period in Months

For each randomized subject:

Study Exposure Period = (EOS date – Randomization Date + 1) / 365.25 * 12

Treatment Emergent Adverse Event (TEAE)

Events categorized as Adverse Events (AEs) starting on or after first dose of investigational product as determined by the flag indicating if the adverse event started prior to the first dose of IP on the Events eCRF and up to 30 days after the last dose of IP date or EOS, whichever occurs first. Please see below for the definition of TEAE in blinded period and OLE.

TEAE	Summary period
Blinded period	Blinded period day 1 (the same as study day 1) through min(last dose date + 30 days, EOS date, the day before OLE day 1)
OLE	OLE day 1 through min(last dose date + 30 days, EOS date)

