10.6 Safety Analyses

10.6.1 Adverse Events

The Medical Dictionary for Regulatory Activities (MedDRA) version 20.1 or later will be used to code all events categorized as adverse events (AEs) to a system organ class and a preferred term. Severity of AEs will be graded using the CTCAE ([Appendix C](#)) and recorded on the eCRF. All adverse event tables will be summarized by actual treatment group. Treatment-emergent adverse events are events with an onset after the administration of the first dose of IP.

The subject incidence of AEs will be summarized for all TEAEs, serious TEAEs, TEAEs leading to withdrawal of investigational product, treatment-related TEAE and fatal TEAEs.

Subject incidence of all TEAEs, serious TEAEs, TEAEs leading to withdrawal of investigational product, and fatal TEAEs will be tabulated by system organ class and preferred term in descending order of frequency.

All TEAEs, serious TEAEs and TEAEs leading to withdrawal of investigational product will also be summarized by subgroups of age (< 65 years, ≥ 65 years; < 75 years, ≥ 75 years) and baseline statin use (Yes, No).

Subject incidence of TEAEs related to a device will be tabulated by preferred term in descending order of frequency.

Subject incidence of adverse events associated with injectable protein therapies:

- Injection site reactions
- Hypersensitivity or allergic reactions

will be summarized by category and preferred term. Neurocognitive events will also be summarized.

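### SAP Table 1 has no OLE Day 1 condition, so open-label adverse events with partial start dates can be counted in the blinded period

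*SAP*

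**What the plan says.** - **When dates are imputed.** SAP Section 9.3.3 covers AE and concomitant-medication start dates. It applies only where "After the issue is queried, the date is still incomplete with year only or year and month only".
- **Day missing.** Table 1 uses the first of the month, with the exception "Default to Study Day 1 if an event starts the same year and month as Study Day 1".
- **Day and month missing.** Table 1 uses 1 January, with the exception "Default to Study Day 1 if an event started the same year as Day 1".
- **Anchor date.** SAP Section 6.1: "Study day 1 is defined as Blinded period day 1". Neither exception refers to OLE Day 1.
- **Period assignment.** SAP Section 6.3 counts a treatment-emergent AE (TEAE) in the blinded period from Blinded Period Day 1 "through min(last dose date + 30 days, EOS date, the day before OLE day 1"), and in the extension from "OLE day 1 through min(last dose date + 30 days, EOS date").
- **eCRF flag.** Section 6.3 identifies onset relative to treatment "as determined by the flag indicating if the adverse event started prior to the first dose of IP on the Events eCRF". That flag says nothing about the OLE boundary.
- **Treatment and tables.** Every subject receives evolocumab in the extension (Protocol Section 2.4). SAP Table 2 plans separate AE summaries for the two periods, grouped by actual blinded-period treatment and without statistical inference.
- **Frozen blinded tables.** SAP Section 10.1 describes the primary analysis as completed, with a data cut-off of 02 November 2017. The final analysis updates the OLE summaries only; the blinded-period analyses are not repeated.

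**The concern.** Table 1 always picks the earliest date that fits the known part of the date, floored at Study Day 1. That keeps an event treatment-emergent, which is the usual aim. Here, however, the date also decides which of two treatment periods the event belongs to, and the earliest compatible date may lie before OLE Day 1 when the true onset was after it.

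Three things follow:

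- In an ezetimibe-arm subject, an event that began on open-label evolocumab is shown under ezetimibe. In all arms, blinded-period incidence is inflated and OLE incidence is reduced. The blinded period is the only randomised comparison of safety and tolerability, which is a stated secondary objective.
- An OLE event first recorded after the primary cut-off, but imputed before OLE Day 1, falls outside the OLE window. The blinded tables are not rerun, so it reaches neither table. This can happen in any arm.
- The same rule dates concomitant medications. SAP Section 10.6.6 summarises lipid-regulating drugs, and changes in them, by study period. A drug started in the extension could appear as a blinded-period change.

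**Working it through.** The plan states no figure on this point, so there is none to reproduce. The check applies Table 1 and the Section 6.3 windows literally.

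**Inputs and assumptions**
- OLE Day 1 is study day 85, the scheduled Week 12 day in SAP Appendix B. The range is 82 to 88, from the ±3-day visit window in the Protocol.
- Onset is uniform over study days 85 to 365, which is 281 days.
- Study Day 1 is uniform over a 365-day year. This is an assumption; the documents give no enrolment pattern.
- The subject stays on blinded treatment to Week 12, so the day before OLE Day 1 is the binding end of the blinded window.

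**Day missing.** An OLE onset moves only if it falls in the calendar month of OLE Day 1 and OLE Day 1 is not the first of that month. If OLE Day 1 is day d of a month of length L, then L − d + 1 onset days move (none if d = 1). Summed over d, this is L(L − 1)/2 per month.
- Sum over the year: 7 × 465 + 4 × 435 + 378 = 5,373.
- Mean per start date: 5,373/365 = 14.7 days, with a maximum of 30.
- Share: 14.7/281 = 5.2% (5.2% to 5.3% over the visit window).

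**Day and month missing.** Let k be the day of the year of Study Day 1, so OLE Day 1 is day k + 84.
- k ≤ 281 (281/365 = 77.0% of start dates): OLE Day 1 is in the same year. The 282 − k OLE days left in that year are set to Study Day 1. Sum: 281 × 282/2 = 39,621.
- k = 282: OLE Day 1 is 1 January, so nothing moves.
- k = 283 to 365: all 281 OLE days fall in the next year and are set to 1 January, before OLE Day 1. Sum: 83 × 281 = 23,323.
- Share: (39,621 + 23,323)/(365 × 281) = 62,944/102,565 = 61.4% (61.0% to 61.8% over the visit window). The Study Day 1 exception contributes 38.6 points and the 1 January default about 23.

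**Reverse direction.** Enumerating every blinded-period onset day gives zero days imputed into the extension.

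**Illustrations (hypothetical dates)**

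| Study Day 1 | OLE Day 1 | True onset | Recorded as | Imputed to |
|---|---|---|---|---|
| 16 Jan 2017 | 10 Apr 2017 | 20 Sep 2017 | 2017 | 16 Jan 2017, blinded |
| 20 Mar 2017 | 12 Jun 2017 | 25 Jun 2017 | Jun 2017 | 1 Jun 2017, blinded |
| 1 Nov 2016 | 24 Jan 2017 | 20 Jun 2017 | 2017 | 1 Jan 2017, blinded |

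**Effect of one moved event.** If it is the subject's first event in that table row, it adds 1/20 = 5.0 points to ezetimibe incidence, or 1/19 = 5.3 points if the 5% not-dosed planning assumption is applied to the 20 planned subjects. In the evolocumab group it adds 1/40 = 2.5 or 1/38 = 2.6 points.

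**The case against.** **The class of events is small.** This stands. The rule applies only after a query has failed, SAP Section 9.3.1 commits to recovering partial data before lock, and Protocol Section 9.2.1 makes onset date a required attribute. A year-only onset should be exceptional. The shares above are conditional on a partial date; they do not forecast a count. Longer gaps between OLE visits (up to 12 weeks) could make partial dates more common there, but the documents give no number.

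**A reader might infer a bias against ezetimibe.** The documents do not support that. Dates move in one direction only, but the rule is identical in every arm and every subject takes evolocumab in the extension. If partial OLE dates occur at the same rate per subject, 2:1 allocation gives matching inflation: 1/19 = 2/38 = 5.3%. What remains is a wrong treatment label in individual ezetimibe subjects, and dilution of the comparison.

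**A reader might also take SAP Section 10.6.1 as a competing definition.** It says "Treatment-emergent adverse events are events with an onset after the administration of the first dose of IP", with no end and no period split. It would put OLE events under ezetimibe only if programmed in place of Section 6.3. Section 6.3 gives explicit windows and notes that the definition was documented before unblinding, and Table 2 requires separate period summaries. The sentence is loose wording, and Section 6.3 governs.

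**Restricting to weeks 12 to 24 gives larger shares.** Over days 85 to 169 they are about 17% (14.7/85) and 88%. But SAP Section 10.1 says the completed primary analysis used all OLE data to the cut-off, so that window is not the one analysed.

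**Any remedy by recording time can err the other way.** This stands. A blinded-period event reported late could be moved into the extension, which the present rule never does. The AE attributes in Protocol Section 9.2.1 also include no visit of recording.

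**Conclusion.** The gap is real and worth correcting, but its practical size is probably small. As written, Table 1 and Section 6.3 together can count an open-label event as a blinded-period TEAE, and never the reverse. Under the assumptions above, this affects about 5% of OLE onsets with the day missing and about 61% with only the year known. An affected event first recorded after the primary cut-off would drop out of both periods' tables.

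The number of partial dates is unknown. The change of about 5 points in ezetimibe incidence holds only for one event that is that subject's first in its row. No net between-arm bias is shown. The AE tables are descriptive, so no error rate or power is affected.

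**What to change.** 1. **Add an OLE Day 1 condition to SAP Table 1**, for AEs and concomitant medications. Where the known part of the date fits both periods, keep the current default if the resolution (or stop) date, or the first eCRF entry in the EDC audit trail, precedes OLE Day 1. Otherwise default to OLE Day 1. AE resolution dates (Protocol Section 9.2.1) and the audit trail (Protocol Section 12.3) are already planned.
2. **List every AE whose partial date fits both periods** and show the counts under both assignments, because late reporting or delayed data entry could push a blinded-period event into the extension.
3. **Apply the rule to the final analysis.** For the completed primary analysis, check for affected AEs and disclose any in the study report. This avoids rerunning unblinded tables under a new rule.
4. **Editorial:** replace the TEAE sentence in SAP Section 10.6.1 with a reference to Section 6.3.

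The cost is a short SAP amendment, modest programming to use the audit-trail date, one listing, and a one-off check of the primary-analysis data. No new data collection is needed.

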9.4 Detection of Bias

This study has been designed to minimize potential bias by the use of randomization of subjects into treatment groups and the use of blinding. It is not expected that any study conduct procedures or statistical analyses will introduce bias in the study results or conclusions. However, potential sources of bias in this study include:

- major protocol deviations likely to impact the analysis and interpretation of the efficacy endpoints
- subject level unblinding before primary database lock and formal unblinding
- DMC related analyses

Important protocol deviations likely to impact the analysis and interpretation of the efficacy endpoints will be tabulated in the Clinical Study Report (CSR).

Any unblinding of individual subjects prior to formal unblinding of the study will be documented in the CSR. The impact of such unblinding on the results observed will be assessed.

For DMC related analyses, details of access to subject level treatment assignments are provided in the protocol, [Section 10.3](#).

Additional sensitivity analyses may be included to assess the impact of potential biases on the primary endpoint. If any sensitivity analyses are required to evaluate potential biases in the study's conclusions, then the sources of the potential biases and results of the sensitivity analyses will be documented in the CSR.

9.5 Outliers

Various methods, including univariate summaries, histograms, scatter plots, box plots, and line graphs, may be used to identify outliers in key safety and efficacy variables. Extreme data points will be identified during the blinded review of the data prior to database lock. Such data points will be reviewed with clinical data management to ensure accuracy. The primary analyses will include outliers in the data. Sensitivity analyses may be undertaken if extreme outliers for a variable are observed.

9.6 Distributional Characteristics

Distributional assumptions for the primary and secondary co-endpoints will be assessed. If the assumptions are not met, then alternative methods will be utilized. The use of alternative methods will be fully justified in the CSR.

9.7 Validation of Statistical Analyses

Programs will be developed and maintained, and output will be verified in accordance with current risk-based quality control procedures.

Tables, figures and listings will be produced with validated standard macro programs where standard macros can produce the specified outputs.

The production environment for statistical analyses consists of Amgen-supported versions of statistical analysis software, for SAS System version 9.2 or later.

10. Statistical Methods of Analysis

10.1 General Principles

The primary analysis will be performed when all randomized subjects in the study have either completed the scheduled study visits up to and including week 24 or have early terminated from the study. At that time, the database of the study will be cleaned,

processed and a snapshot will be taken. The study will be unblinded. Based on the snapshot for the primary analysis, efficacy and safety analyses will be performed on the FAS. Unless otherwise specified, the FAS will be the default analysis set for the primary analysis and data will be summarized by randomized treatment group assignment and by pooled frequency for evolocumab and pooled ezetimibe. The treatment effect of evolocumab compared to ezetimibe will be evaluated for all efficacy endpoints through the Week 12 visit. In addition, descriptive analyses from the open-label extension (weeks 12 to 24) will be performed on OLEAS. **Please note that for the completed primary analysis, data collected for the open-label extension period was expanded beyond weeks 12 to 24. All available data from the open label extension period, as of the data cut-off date 02 November 2017, were included for the open-label extension period analyses in the primary analysis.**

The final analysis will be conducted when all enrolled subjects have either completed the scheduled visits or have early terminated from the study. At that time, the database of the study will be cleaned, processed and **locked**. Based on the **locked database**, long-term efficacy and safety analyses will be performed on OLEAS and the analyses will be descriptive. **The descriptive analyses for the open-label extension period in the primary analysis will be updated using the data from the final database lock. All analyses for blinded period in primary analysis will not be repeated.**

Subject disposition, demographics, baseline characteristics, and exposure to IP will be summarized.

Summary statistics for continuous variables will include the number of subjects, mean, median, Q1, Q3, standard deviation or standard error, minimum, and maximum. For categorical variables, the frequency and percentage will be given.

Missing data will not be imputed for safety endpoints.

[figure not shown]
A summary of the analyses for each part of the study can be found in [Table 2](#).

Table 2. Analyses Summary

Analyses	Double-blind Period	OLE Period
Efficacy	
 Summary by randomized treatment group in blinded period 
For co-primary and co-secondary endpoints:
 
 Repeated measures model Cochran Mantel-Haenszel test for LDL-C achievement Multiplicity adjustment 	
 Summary by randomized treatment group in blinded period / evolocumab in OLE period No statistical inference
AE, Safety lab	
 Summary by actual treatment group in blinded period No statistical inference 	
 Summary by actual treatment group in blinded period / evolocumab in OLE period No statistical inference

Multiplicity Adjustment Method

Methods of adjusting for multiplicity due to multiple endpoints (co-primary and co-secondary efficacy endpoints) in order to preserve the familywise error rate at 0.05 are described in the diagram below.

Testing of each co-endpoint pair for the pooled evolocumab vs. pooled ezetimibe analysis will result in a single p-value, and for co-secondary endpoints these p-values

will then be used in the Hochberg procedure. The following test procedure will be used to preserve the familywise error rate for the co-primary and co-secondary endpoints:

1. If the treatment effect from the primary analysis of the co-primary endpoints are both significant at a significance level of 0.05, statistical testing of the tier 1 co-secondary efficacy endpoints will follow the Hochberg procedure at a significance level of 0.005 ([Hochberg, 1988](#)).
2. If all tier 1 co-secondary efficacy endpoints are significant, the tier 2 co-secondary efficacy endpoints will be tested using the Hochberg procedure at a significance level of 0.05.
3. If not all tier 1 co-secondary efficacy endpoints are significant, the tier 2 co-secondary efficacy endpoints will be tested using the Hochberg procedure at a significance level of 0.045 ([Wiens, 2003](#)).

Unless specified otherwise, all other hypothesis testing will be 2-sided with a significance level of 0.05.

